11.2	SAMPLE SIZE DETERMINATION	29
11.3	DATA MANAGEMENT	ERROR! BOOKMARK NOT DEFINED.
12	DATA HANDLING AND RECORD KEEPING	31
12.1	PHI AND HIPAA	31
12.2	CONFIDENTIALITY	31
12.2.1	ACCESS TO SOURCE DOCUMENTS	31
12.2.2	SENSITIVE INFORMATION	31
12.2.3	OTHER.....	31
12.3	SOURCE DOCUMENTS	32
12.4	DATA MANAGEMENT RESPONSIBILITIES	32
12.5	DATA CAPTURE METHODS.....	33
12.6	PROTOCOL DEVIATIONS	33

12.7	RECORD RETENTION	33
13	ETHICAL CONSIDERATIONS	34
13.1	ETHICAL STANDARD	34
13.2	INSTITUTIONAL REVIEW BOARD (IRB)	34
13.3	INFORMED CONSENT PROCESS	34
13.4	EXCLUSION OF WOMEN, MINORITIES, AND CHILDREN (SPECIAL POPULATIONS)	35
13.5	PARTICIPANT CONFIDENTIALITY	35
13.6	STUDY DISCONTINUATION	35
14	PUBLICATION POLICY	36
15	LITERATURE REFERENCES	37
	APPENDIX A: SCHEDULE OF EVENTS	39
	APPENDIX B: AE REPORT FORM	39
	APPENDIX C: IRB AMENDMENT TRACKING LOG	42
	APPENDIX D: AE REPORT FORM	43
	APPENDIX F: NOTE TO FILE	47
	APPENDIX G: TELEPHONE SCRIPT	49
	APPENDIX H: TRAINING LOG	51

LIST OF ABBREVIATIONS

AE	Adverse Event/Adverse Experience
ANOVA	Analysis of Variance
CFR	Code of Federal Regulations
CNS	Central Nervous System
Co-I	Co-Investigator
CRF	Case Report Form
CTRC	Clinical Trials Research Center
DMV	Department of Motor Vehicles
eCRF	Electronic Case Report Form
EEG	Electroencephalogram
FDA	Food and Drug Administration
GCP	Good Clinical Practice
HIPAA	Health Insurance Portability and Accountability Act
Hz	Hertz
ICF	Informed Consent Form
LAR	Legally Authorized Representative
NIH	National Institutes of Health
NRB	Neurosciences Research Building
OHRE	Office of Human Research Ethics
OHRP	Office for Human Research Protections
PHI	Protected Health Information
PI	Principal Investigator
SAE	Serious Adverse Event/Serious Adverse Experience
tACS	Transcranial Alternating Current Stimulation
tDCS	Transcranial Direct Current Stimulation
TMS	Transcranial Magnetic Stimulation
UE	Unexpected Event
UNC	University of North Carolina
UNC-CH	University of North Carolina at Chapel Hill
US	United States

STUDY SUMMARY	
Title	A pilot, randomized, double-blind, crossover study investigation the effects of 10Hz transcranial alternating current stimulation on the immune response to psychological stress
Short Title	AIMS
Protocol Number	Version 1.1
Phase	Pilot
Methodology	Double-blind, randomized, active sham controlled
Study Duration	This study will take two months to complete.
Study Center(s)	This is a single-site study performed at the University of North Carolina at Chapel Hill.
Objectives (Purpose)	The primary objective of this study is to explore the effects of alpha oscillations on the relationship between the immune system and stress response.
Number of Subjects	20
Diagnosis and Main Inclusion Criteria	Eligible participants will be healthy adults between the ages of 18-35 with no history of autoimmune disease or mental or psychiatric disorder.
Description of Intervention (Procedures/methods)	The participants will be randomized into one of two arms: either 40 minutes of sham tACS or 40 minutes of 10 Hz tACS while in a relaxed, yet experimentally controlled state, by watching a nature movie such as "Reefscape" during stimulation.
Related IRB Applications	N/A

1.4 FUNDING SOURCES

Please list below the funding sources for this project:

Sponsor Name	UNC Ramses Number	Sponsor Type	Prime Sponsor Name	Prime Sponsor Type	Sponsor/Grant Number
NIH National Institute of Mental Health (NIMH)	N/A	Federal	N/A	N/A	R01MH101547

External Funding: This project is externally funded but UNC-CH is not the direct recipient of federal funds.

UNC-CH Funding: This project is not funded through UNC-CH.

Classified: This project is not classified.

2 INTRODUCTION

This document is a protocol for a human research study. This study is to be conducted according to U.S. and international standards of Good Clinical Practice (FDA Title 21 Part 312 and International Conference on Harmonization guidelines), applicable government regulations and Institutional research policies and procedures.

2.1 BACKGROUND

The field of psychoneuroimmunology investigates to the interaction between the brain and the immune system, regulated by psychological and behavioral factors (Kiecolt-Glaser et al, 2002). There are two components of the immune system: innate immunity, which generally responds to threats, and adaptive immunity, which forms specific responses to invaders up to days after the target is recognized (Segerstrom & Miller, 2004). Studies in psychoneuroimmunology have found decreased adaptive immune functioning in individuals subjected to ongoing stress, such as medical students who are administered vaccinations during ongoing periods of high stress (Kiecolt-Glaser et al, 2002). However, lab-induced stressors produce a quick change in markers of innate immunity.

Upon encountering an acute psychological stressor, such as a scary movie or difficult exam, the sympathetic nervous system activates to ready the body for action. Often called the “fight or flight” response, this activation includes heart rate elevation, increased sweat secretion, and vasoconstriction of blood vessels (Segerstrom & Miller, 2004). These effectors are stimulated by norepinephrine, a neurotransmitter that binds to adrenergic receptors on target cells to carry out the sympathetic response. Natural killer (NK) cells – one of the primary components of innate immunity – also have adrenergic receptors; therefore, a sympathetic response to a stressor also stimulates NK activity. Studies involving lab-induced stressors have demonstrated this relationship through a correlation between norepinephrine and NK activity (Schedlowski et al, 1993). Immediately after the stressor, NK levels rise to almost double the baseline value, a peak that is accompanied by a similar rise in norepinephrine levels. Within an hour, NK activity drops to a level significantly below baseline, as the effects of the stressful event and sympathetic activation returns to normal. If this process is repeated, such as during exams or other periods of prolonged acute stress, the fluctuations in NK activity can lead to issues in immune functioning (Kiecolt-Glaser et al, 2002).

2.2 INVESTIGATIONAL AGENT

Transcranial Alternating Current Stimulation (tACS) is one method that has been demonstrated to enhance alpha oscillations in healthy participants by applying weak electrical currents to the scalp to modulate rhythmic brain activity patterns (Lustenberger et al, 2015). Alpha oscillations, which occur in frequencies between 8-12Hz, have been correlated with a relaxed emotional state, and EEG recordings of individuals who are meditating show an increase in alpha in the frontal lobe (Lagopoulos et al, 2009; Takahashi et al, 2005). Additionally, this increase in alpha during meditation has been negatively correlated with sympathetic activation, further supporting a relationship between alpha oscillations and decreased stress.

2.3 DOSE RATIONALE

10Hz tACS will be applied because this frequency corresponds with the alpha band of 8-12Hz and will therefore increase alpha oscillations. This increase should produce a decreased sympathetic stress response, as indicated by the previously mentioned relationship between alpha and the sympathetic nervous system.

2.4 STUDY AIMS/HYPOTHESES

NULL HYPOTHESIS. 10Hz tACS does not decrease immune response compared to active sham.

ALTERNATIVE HYPOTHESIS. 10Hz tACS decreases immune response compared to active sham.

3 SUBJECT SELECTION AND WITHDRAWAL

A total of 20 participants will be recruited for this study and all data will be collected at UNC-CH. No specific plans have been made to enroll participants from vulnerable populations.

3.1 INCLUSION CRITERIA

In order to be eligible to participate in this study, a participant must meet all of the following criteria:

- Between the ages of 18 and 35 years
- Capacity to understand all relevant risks and potential benefits of the study (informed consent)
- Willing to comply with all study procedures and be available for the duration of the study
- Speak and understand English

3.2 EXCLUSION CRITERIA

A potential participant who meets any of the following criteria will be excluded from participation in the study:

- Diagnosis of eating disorder (current or within the past 6 months)
- Diagnosis of OCD (lifetime)
- ADHD (currently under treatment)
- Neurological disorders and conditions, including, but not limited to:
 - History of epilepsy
 - Seizures (except childhood febrile seizures and ECT-induced seizures)
 - Dementia
 - History of stroke
 - Parkinson's disease
 - Multiple sclerosis
 - Cerebral aneurysm
 - Brain tumors
- Medical or neurological illness or treatment for a medical disorder that could interfere with study participation (e.g., unstable cardiac disease, HIV/AIDS, malignancy, liver or renal impairment)
- Prior brain surgery
- Any brain devices/implants, including cochlear implants and aneurysm clips
- Traumatic brain injury
- (For females) Pregnancy or breast feeding
- Personal or family history of mental/psychiatric disorder (e.g., anxiety, major depressive disorder, schizophrenia, etc.)
- Diagnosis of an autoimmune disorder
- Failure to pass a urinary drug test at the first session.
- Anything that, in the opinion of the investigator, would place the participant at increased risk or preclude the participant's full compliance with or completion of the study

Justifications for any exclusions based on race, gender, or ethnicity: Non-English speaking individuals are excluded because the ability to accurately and completely communicate study information, answer questions about the study, and obtain consent are necessary.

Justification for excluding women or women who become pregnant: Pregnant participants will be excluded despite the fact that theoretical risk to mother or fetus is exceedingly small, since no safety data for pregnancy is known to exist for tDCS/tACS studies. We will verify pregnancy status via a urine pregnancy test for all female participants prior to receiving treatment on Day 1 of Stimulation.

3.3 STRATEGIES FOR RECRUITMENT AND RETENTION

3.3.1 RECRUITMENT

The target population of this study includes healthy individuals between the ages of 18 to 35 pulled from UNC Chapel Hill and the surrounding area, including approximately 30,000 candidates for participation. Recruitment will occur via two methods: flyers to be distributed at major locations on the campus (libraries, gyms, classroom buildings, etc.) and a mass email to all individuals with a UNC-affiliated email address.

3.3.2 RETENTION

The retention strategy includes a payment schedule of two times per participant, corresponding with the two sessions. The second session will involve a bonus payment for completion of the study. Research staff will send participants a reminder text the day before each session, and will be available by email and phone at all times.

[figure not shown]
4 BASIC STUDY DESIGN

The design for this study is a pilot, randomized, double-blind, sham-controlled, clinical trial which will be used to demonstrate feasibility and collect effectiveness data for further refinement of a tACS approach and for the subsequent design of a follow-up, multi-site, large scale study. We are seeking 20 healthy participants, both male and female, between the ages of 18-65. All women of child-bearing potential will be asked to take a pregnancy test during the initial session in order to determine eligibility for the study.

This is a double-blind, randomized crossover study. We estimate 2 months to complete study enrollment.

Participants will be randomly assigned to one of 2 arms.

Figure 1.

Active sham treatment will include 10 seconds of ramp-in to 1 minute of 10 Hz tACS with a ramp-out of 10 seconds for a total of 80 seconds of stimulation. The choice of an active sham is motivated to enhance success of patient blinding by mimicking skin sensations associated with tACS. 10 Hz tACS will have a 10 second ramp-in and ramp-out with 40 minutes of stimulation for a total of 2420 seconds of stimulation. Stimulation waveform is a sine-wave with peak-to-peak amplitude of 2 mA. In both arms, participants will stay in a relaxed yet controlled state by watching a nature movie (“Reefscape”) during stimulation.

Eligible participants will have a total of 2 visits, each lasting approximately 3 hours and separated by at least 1 week. Total participation will include about 6 hours over the course of two weeks. All time estimates take into consideration breaks and time variance in administration.

4.1 TREATMENT ASSIGNMENT PROCEDURES

Participants will be randomized into one of 2 arms (*see Figure 1 above*). This is a double-blind study, so neither the participant nor the research will know which treatment the participant is receiving, if any.

4.1.1 RANDOMIZATION PROCEDURES

[name] will randomize 40 6-digit stimulation codes which will be used by the study coordinator and research assistants and will be linked to the participant numbers of enrolled participants. These stimulation codes are directly linked to which treatment participants receive (sham or 10 Hz tACS) at each session, and will be used with the XSCITE 100 stimulator. An unblinded code sheet that matches these stimulation codes to treatment arm will be kept by [name] and will not be available to the study coordinator or research assistants.

The unblinded code sheet will have the following information:

1. The initial identifier codes for all potential participants
2. Stimulation code: 6-digit numerical code for the stimulation session
3. Condition number: Numerical code for the condition
4. Condition name: Name of the condition

A copy of this code sheet with condition number and condition name REMOVED is provided to the study coordinator and research assistants. This blinded code sheet will be used to ensure the correct stimulation code is provided for each session.

These linked codes ensure that the study coordinator and research assistants are kept blinded to which treatment each participant receives. Please see *Data and Safety Monitoring* for more information on unblinding this information.

5 STUDY SCHEDULE

It is important to note that consent, scales, and experiments will all take place in a private room. Any phone calls will take place in a private lab environment as well.

5.1 SCREENING

The screening process will involve a telephone call with the potential participant to inform of expectations and determine eligibility. A researcher will conduct a screening with each participant prior to scheduling the first session. If a participant is determined to be ineligible, data from the screening will be retained.

5.2 STIMULATION SESSIONS

Participants will undergo two sessions with the same procedure; the only change will be the stimulation condition.

5.4.1 SESSION 1

In the initial session, participants will be explained the procedure and reminded of their expectations and rights (informed consent). After obtaining consent, a urine drug test and pregnancy screening will be administered. Once they are both determined to be negative, the stimulation, EEG, and heart rate electrodes will be applied. Participants will then undergo a ten-minute resting state block to record EEG activity. Participants then provide a baseline saliva sample and receive 40 minutes of either 10Hz tACS or sham stimulation (depending on the randomized condition) while watching the 'Reefscape' video. After the stimulation, the participant will complete the stimulation adverse effects questionnaire, and will then provide a final saliva sample. The study coordinator will remove all equipment, and the participant will fill out the final two questionnaires and receive \$20 in compensation.

5.4.2 SESSION 2

The procedure for the second session will follow the same timeline as the first, with the exclusion of informed consent, urine drug test, and pregnancy screening processes. Participants will receive \$40 in compensation at the end of this session.

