7.3 PREPARATION AND ADMINISTRATION OF STUDY INVESTIGATIONAL PRODUCT

After participants have completed the questionnaires, they will be comfortably seated. The research team will first measure their heads electrode placement using the 10-20 system. Participants will then be fitted with the 3 electrodes for stimulation. The participant will be in the relaxed yet, experimentally controlled state by watching a nature movie. One session of stimulation will be performed per visit for 40 minutes. During the 10 Hz tACS

condition, participants will have a 10 second ramp in and ramp out with 40 minutes of stimulation for a total of 2420 seconds. Stimulation waveforms are sine-waves with a peak-to-peak amplitude of 2 mA. The sham stimulation will include 10 seconds of ramp in to 1 minute of 10 Hz tACS with a ramp out of 10 seconds for a total of 100 seconds of stimulation. Electrodes will be saline soaked, 5x5cm and placed over F3 and F4 with a 5x7cm placed over CZ as a return electrode.

Stimulation devices will be preprogrammed and codes will be randomized to one of the two experimental arms. Researchers will enter the participant-specific code into the App that controls the stimulation and monitor participants during the 40 minutes of the stimulation.

The study coordinator and/or the research assistant will be thoroughly trained and have trainings documented on the transcranial stimulation device and will be present during all stimulation sessions. *Please see Appendix F for an example of the training documentation log.* To monitor side effects of stimulation a questionnaire will be administered after each stimulation session. *Please see Attachment 1 for an example of the stimulation questionnaire.*

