8.2.2 PHYSICAL

Risk of Injury and Discomfort: Transcranial current stimulation has been used without any reports of serious side-effects for more than a decade. This stimulation made has NOTHING to do with electroconvulsive therapy that applies many orders of magnitude higher stimulation current. Rather, transcranial current stimulation is so weak that it does not cause super-threshold activation of neurons ([name] and McCormick, 2010). In particular, tACS has been used without reports of any serious side-effects. Some participants report a transient mild tingling, burning, or itching underneath the electrodes and headache, but no other side effects have been noted. Importantly, it remains unclear if these mild side-effects were caused by the transcranial brain stimulation. In order to monitor these side-effects, we will be administering an adverse effects stimulation questionnaire after each stimulation session to determine whether these effects were experienced. Research personnel present during these sessions will also check in with the participant periodically during the stimulation to see whether they are comfortable. If any side-effect occurs (rated by the participant as stronger than “moderate”) or the participant is experiencing severe discomfort, the stimulation will be immediately stopped.

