10.1 SAFETY PARAMETERS

STIMULATION SIDE EFFECTS. A stimulation adverse effects questionnaire used in previous studies will be administered at the end of each stimulation session. This questionnaire will be used as a safety measure and to collect data on participant experience. The adverse effects questionnaire asks participants to respond on a 4 point Likert scale on the severity of symptoms experienced during the stimulation session (1 = absent, 2 = mild, 3 = moderate, 4 = severe). The side effects listed are headache, neck pain, scalp pain, tingling, itching, ringing/buzzing noise, burning sensation, local redness, sleepiness, trouble concentrating, improved mood, worsening of mood, dizziness, flickering lights, and other (specify). Participants are also asked to rate on a 5 point Likert scale how related they believe the side effects to be to stimulation (1 = no relation, 2 = remote, 3 = possible, 4 = probable, 5 = definite).

In addition to this survey, the study coordinator or research assistant will periodically check in with the participant during the stimulation session to assess side effects.

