APPENDIX A: SCHEDULE OF EVENTS

	Phone Screening	Day 1 of Stimulation	Day 2 of Stimulation
Procedures			
Provide Verbal Consent	x		
Signed Consent Form		x	
Assessment of Eligibility Criteria	x	x	
Urine Pregnancy Test		x	
Urine Drug Test		x	
Baseline Assessments (PSS, CD-RISQ, PSQI)		x	
Saliva Sample		x	x
Stimulation		x	x
Stimulation Questionnaire		x	x
Saliva Sample		x	x
Final Questionnaires (PANAS, STAI)		x	x

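### The adverse-effects questionnaire, including its local-redness item, is completed before the electrodes come off and no later skin check is scheduled, so redness under the pads may be under-recorded

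*Combined protocol and SAP*

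**What the plan says.** The session order is in section 5.2, under the subheading 5.4.1 Session 1. Once the 40 minutes are over: "After the stimulation, the participant will complete the stimulation adverse effects questionnaire, and will then provide a final saliva sample". The next sentence reads: "The study coordinator will remove all equipment, and the participant will fill out the final two questionnaires". Session 2 (5.4.2) "will follow the same timeline as the first", apart from consent and the urine tests.

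Appendix A lists the row "Stimulation Questionnaire" between stimulation and the second saliva sample on both days. It has no row for electrode removal or for looking at the skin.

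Section 10.1 describes the questionnaire as a self-rating on four points, from absent to severe. Its items include "burning sensation, local redness, sleepiness, trouble concentrating". No response for an item that could not be assessed is described.

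Section 7.3 gives the montage: two 5x5 cm electrodes "placed over F3 and F4 with a 5x7cm placed over CZ as a return electrode".

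Section 6.3 calls the questionnaire a safety measure. Section 8.3 uses its moderate and severe ratings to start a staff discussion, and the reported intensity to decide on contact with the principal investigator.

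**The concern.** Most items on the questionnaire are sensations or states that the participant can report with the equipment in place. Local redness is different, because it is a visible sign and someone has to look at the skin. As sequenced, the item is answered at a point in the visit when neither the participant nor the coordinator can see the skin under the pads, and nothing scheduled later returns to it.

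What is at stake is the quality of one safety item and the review that depends on it. A reaction that shows only when the pads come off would not be reflected in a rating already given, so it would not reach the review in section 8.3 by that route. A pilot meant to inform a larger trial would then carry forward a redness record that tends to read low in both conditions.

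**Working it through.** The plan gives no figure to reproduce here. The check sets the sections side by side, with two simple counts.

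**1. Is the order consistent across the documents?**

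| Place | Position of the questionnaire |
|---|---|
| 5.4.1 | After stimulation, before the final saliva sample; removal of equipment comes later |
| 5.4.2 | Same as session 1 |
| Appendix A | After stimulation, before the second saliva sample, both days |
| 6.3, 10.1 | At the end of the stimulation session; not placed relative to removal |
| 7.3, 8.3 | After the stimulation session; not placed relative to removal |

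Only 5.4.1 and 5.4.2 fix the position relative to removal. Nothing elsewhere contradicts them.

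**2. Does any later step look at the skin?** After removal the participant completes two questionnaires, which Appendix A names as PANAS and STAI. Section 6.1 describes these as measures of affect and anxiety. The staff check-ins in 8.2.2, 8.3 and 10.1 take place during stimulation, with the pads on. Follow-up under 10.4 starts only after an adverse event has been identified. No scheduled safety observation comes after removal.

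**3. Which items are affected?** Section 10.1 names 14 effects plus an open item. Scalp pain, tingling, itching and burning are felt and can be rated with the pads on. Of the named effects, local redness is the one that depends on seeing the skin.

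**4. Counts.**
- Questionnaires completed in this order: 20 participants x 2 sessions = 40. Each participant has one session of each kind, so 20 fall under 10 Hz tACS and 20 under sham.
- Skin covered by stimulation pads at the time of rating: 5x5 + 5x5 + 5x7 = 25 + 25 + 35 = 85 cm2, the same in both conditions.

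These counts show how widely the sequence applies. They do not measure how often redness occurs or is missed, and the documents contain nothing from which that could be calculated.

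**The case against.** The strongest reply is that a reaction seen at removal need not be lost. Section 10.2.1 requires every adverse event, local reactions included, to be entered on a case report form and an adverse-event form whatever its cause. The coordinator who takes off the equipment also completes those forms, and both the principal investigator and the co-investigator review them. The participant is still in the room, completing two more questionnaires. This stands as a real second route. It is a passive one, however: it asks nobody to look, does not use the four-point scale, and does not correct a redness rating already given.

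A second reply is that the end of the session in 6.3 and 10.1 could mean the end of the visit, after removal. Taken alone those sections allow it, but 5.4.1 is specific and Appendix A agrees that the questionnaire precedes the saliva sample.

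Four stronger readings are tempting, and the documents do not support them:
- **Redness will be scored as absent.** No rule for an unobservable item is given, and the form is an attachment that is not part of the text. A participant might leave the item blank, ask staff, or answer from sensation.
- **Skin reactions in general are missed.** The physical effects named in 8.2.2 are sensations ("Some participants report a transient mild tingling, burning, or itching underneath the electrodes and headache"), and these can be rated with the pads in place.
- **More serious skin damage would go unrecorded.** The documents mention no such injury, and 10.2.1 would cover one that was noticed.
- **A planned tACS-versus-sham comparison is spoiled.** Section 11 names biomarkers as primary and EEG as secondary outcomes, and specifies no comparison of any questionnaire item.

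**Conclusion.** The point holds in a limited form. Followed as written, the plan has local redness rated while the skin under the stimulation pads is covered, at both sessions, with no later rating or inspection scheduled. Redness under the pads may therefore be under-recorded in both conditions. If anyone did compare the conditions on this item, low counts in both could hide a difference.

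The extent is one item on each of 40 planned forms; the number of reactions missed is unknown. The conclusion assumes that staff follow the order in 5.4.1 and that the attached form has no instruction to return to the item after removal. If it has one, the remaining task is to bring the protocol text into line with it.

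This is a minor safety-measurement weakness with a cheap remedy. It has no bearing on the cytokine, alpha-amylase or cortisol analysis.

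**What to change.** In sections 5.4.1, 6.3 and 10.1, keep the questionnaire where it is and add one step: once the electrodes are off, after the final saliva sample, the local-redness item is rated or re-rated on the same four-point scale, with the coordinator looking at the three pad sites. State that this later rating is the one recorded and that it enters the existing review of questionnaire responses in 8.3. Add the step to Appendix A for both days. Session 2 inherits it through 5.4.2.

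The saliva timing does not move, and no extra visit, staff or equipment is needed. The time cost is under a minute per session, by someone already removing the pads.

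The downside is to blinding. A formal look at the skin may give the coordinator and the participant a hint of the condition before PANAS and STAI are completed. In a two-period crossover, a hint at session 1 also points to the condition at session 2, and placing the check after the saliva sample does not remove either effect. The added risk is modest: removal exposes the skin in any case, and the primary outcomes are laboratory assays.
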